Comment on if the proposed change(s) require a modification to the Consent Form (CF)

The changes require minor modifications to the CF, which have been made.

Application for Continuation of Research

Status

Current Status of Study:

Subject enrollment is ongoing.

Summary of Experiences to Date

Please provide a summary of scientific progress of the study and the experience of research participants, to date. This requirement is designed to allow for the investigator and the IRB to reassess the study's risks and benefits in terms of developments in the field, changing practice patterns, and new IRB policies and procedures.

Five subjects have enrolled the study of which one is currently enrolled and two have completed without complications. Two subjects decided to discontinue study involvement due to changes in employment that made them unable to commit the time necessary to complete the study.

Funding

Have there been any changes in funding status since the prior approval?

No

Have the principal investigator and other investigators made all required disclosures of financial interest in the study sponsor/product?

Yes

Summary

Have there been any study findings, recent literature, or untoward events occurring here or at other sites in the past year which might affect the analysis of the safety, risks or benefits of study participation?

No

Have there been any serious adverse events (serious and/or unanticipated problems involving risks to subjects or others at this site which occurred in the past year)?

No

Have all study staff with a significant role in the design or implementation of the human subject components of this study received required training in human research subject protections?

Yes

Is the study covered by a certificate of confidentiality?

No

Overall Progress

Approved sample size

20

Total number of participants enrolled to date

5

Number of participants who have completed the study to date

2

Have there been any significant deviations from the anticipated study recruitment, retention or completion estimates?

No

Comments / additional information

Sample Demographics

Specify population

Adults with Obsessive-Compulsive Disorder

Total number of participants enrolled from this population to date

4

Gender, Racial and Ethnic Breakdown

2 Female, 3 Males. 4 White, 1 Other. 1 Hispanic, 4 Non-Hispanic.

Summary of Current Year's Enrollment and Drop-out

Number of participants who signed consent in the past year

5

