The need to understand the impact of smoked THC and CBD in clinical populations is supported by 3 prior studies by Valerie Curran’s group at University College London. In a 2008 study, hair samples collected from a population of 140 users of a variety of illicit substances were screened for THC and CBD. Subjects who screened positive for THC alone showed higher levels of positive schizophrenia-like symptoms compared to both those who screened negative for cannabinoids and those who screened positive for THC and CBD, suggesting that smoked CBD may have antipsychotic properties. A second study in 2010 in which subjects were assessed after using their chosen strain of cannabis indicated that smokers of high CBD:THC strains showed a decreased attentional bias towards drug and food stimuli and less self-reported liking of cannabis stimuli. These data suggest that CBD may mitigate the effects of THC and may have utility as a treatment for cannabis dependence. Finally, in a 2014 study of 48 cannabis-using subjects who received inhaled THC, CBD, THC+CBD, and placebo, subjects showed improved recognition of facial affect without any effect on feelings of being “stoned” after receiving CBD alone. In contrast, THC produced a reduction in facial affect recognition, while THC+CBD and placebo showed no effect. Both THC alone and THC+CBD in combination increased feelings of being “stoned” relative to placebo. The results of this laboratory study provide early evidence that agents that target the endocannabinoid system may produce contrasting neurocognitive effects. In total, the findings from these studies suggest that further study of the impact of THC and CBD in psychiatrically ill populations (including OCD) is warranted.

Specific Aims and Hypotheses

Specific Aims and Hypotheses

Specific Aims:

To compare the effects of High THC (5-10%)/Low CBD (<1%) marijuana, Low THC (<1%)/High CBD (>10%) marijuana, and placebo (0% THC and CBD) marijuana in adults with primary OCD who also occasionally smoke marijuana.

Specific Hypothesis:

In the acute setting, smoked marijuana in both high THC/low CBD and low THC/high CBD concentrations will lead to a reduction in symptoms in adults with primary OCD who are also occasional marijuana smokers as compared to placebo.

Description of Subject Population

Sample #1

Specify subject population

Adults who meet DSM 5 criteria for OCD who are also occasional marijuana smokers

Number of completers required to accomplish study aims

15

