
Projected number of subjects who will be enrolled to obtain required number of completers

20

Age range of subject population

21 - 55

Gender, Racial and Ethnic Breakdown

Based on the community from which we will be drawing patients and proportions to those encountered during previous clinical trials at this site, we expect the sample to be approximately 5 percent Hispanic and 95 percent Non-Hispanic. Racially, we expect there will be 89 percent White, 9 percent Black, 2 percent Asian. Based upon the prevalence of OCD, it is expected that the sample will be approximately 1 to 1 = male to female.

Description of subject population

The sample will consist of a maximum of 15 female and male adults with a diagnosis of OCD and clinically significant symptoms (i.e., a Y-BOCS score of at least 16) who are also occasional marijuana smokers. Subjects may or may not be seeking treatment for their OCD but will not be seeking treatment for their marijuana use. ~~Minorities and females will be well represented in this study.~~

Recruitment Procedures

Describe settings where recruitment will occur

Recruitment will draw from the broadest possible population with respect to gender and ethnic origin. IRB-approved radio/internet/newspaper advertisements and flyers will be used to recruit subjects (materials to be submitted).

We will also use various internet sites (e.g., Twitter, Google advertising, Craigslist, Facebook, LinkedIn, Research Match, Bangitout.com, Clinicaltrials.gov, twitter, Psychology Today, Craigslist, and other similar sites) as additional recruitment tools.

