Cannabis Effects: We will use a random-effects linear mixed model to evaluate changes in each continuous outcome (YBOCCS, OCD-VAS, STAI-S MRF, cardiovascular measures) as a function of condition (THC, CBD, placebo), time point, and their interaction. Mixed-effects modeling accounts for clustering of repeated measures within subjects, allows time to be modeled as a continuous rather than categorically, and has been used in similar acute pharmacological challenge studies (Rodriguez et al. 2013). The model will include participants as a random effect, condition and time as fixed within-subjects factors, the interaction between condition and time, and a random intercept. Given that the interval between sessions increases over the course of each session, we will model time as a continuous variable. We will use contrasts within each mixed-effects linear regression model to estimate differences in outcomes between both active cannabis varieties and placebo at different time points. All statistical tests will be conducted using an alpha level of 0.05, two-tailed.

Other Effects: Though we have no a priori hypotheses about the effects of age, gender, comorbid diagnoses (e.g. MDD), or other factors that might influence our participants' response to cannabis, we will nonetheless explore the possibility of such effects by including these factors as covariates in separate analyses.

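### The sample is given as 20 enrolled in two places and as at most 15 in a third; read as an enrolment cap, 15 can no longer yield the 15 completers required.

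*Combined protocol and SAP*

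**What the plan says.** Under Description of Subject Population, Sample #1, the entry for "Number of completers required to accomplish study aims" is 15. The entry for "Projected number of subjects who will be enrolled to obtain required number of completers" is 20. The free-text description of the population in the same section then says: "The sample will consist of a maximum of 15 female and male adults with a diagnosis of OCD".

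In the Application for Continuation of Research, under Overall Progress, "Approved sample size" is 20. The Summary of Experiences to Date reports: "Five subjects have enrolled the study of which one is currently enrolled and two have completed without complications". It adds: "Two subjects decided to discontinue study involvement due to changes in employment". The form then asks: "Have there been any significant deviations from the anticipated study recruitment, retention or completion estimates". The answer given is No.

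No dropout rate is stated. Neither the population section nor the Data Analytic Plan gives an effect size, standard deviation or power behind the figure of 15.

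**The concern.** Enrolment and completion are different quantities, and the documents keep them apart in the numbered entries (20 and 15). The narrative sentence does not. It describes the sample by diagnosis, symptom score and marijuana use, which are entry criteria, and then limits it to 15. Taken literally, it limits the number who enter.

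Fifteen completers is the only planning figure in the documents, and it is described as what the aims require. If recruitment stopped at 15 enrolled, the trial would end below that size by construction. If recruitment runs to 20, the size is attainable, but the margin for further loss is smaller than the plan began with. A reader of the eventual report needs to know which limit applied and what number of completers was realistic.

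**Working it through.** **Inputs**

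- Completers required: 15 (Sample #1).
- Projected enrolment: 20 (Sample #1); approved size: 20 (Overall Progress).
- Limit in the population description: 15.
- To date: 5 enrolled, 2 completed, 2 discontinued, 1 still in the study (Summary of Experiences to Date). Sample Demographics also gives 4 enrolled from this population, but its sex breakdown (2 + 3) and race breakdown (4 + 1) each sum to 5, so 5 is used here.

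**1. The plan's own pair.** Implied completion is 15/20 = 75%, and 15/0.75 = 20. The two figures agree with each other. Because the rate is solved from the same pair, this shows coherence and is not an independent check.

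**2. If 15 is an enrolment cap.** At the outset, 15 completers from 15 enrolled needs 15/15 = 100% completion. With 2 already lost, the maximum is 15 − 2 = 13 completers, so the chance of reaching 15 is zero at any future retention. Outcomes still open under this cap: 15 − 4 = 11. Expected completers at 75% are 2 + 11 × 0.75 = 10.25.

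**3. If 20 are enrolled.** Outcomes still open: 20 − 4 = 16 (1 current participant and 15 still to enrol). Completers still needed: 15 − 2 = 13. Required completion is 13/16 = 81%. With X binomial (16, p), the chance of success is P(X ≥ 13), and expected total completers are 2 + 16p:

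| Later completion p | P(X ≥ 13) | Expected total completers |
|---|---|---|
| 0.75 | 0.40 | 2 + 12.0 = 14.0 |
| 0.60 | 0.07 | 2 + 9.6 = 11.6 |
| 0.50 | 0.01 | 2 + 8.0 = 10.0 |

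For comparison, before anyone entered, the chance of at least 15 of 20 completing at 75% was 0.62.

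**4. How much the retention so far can say.** Observed completion is 2/(2 + 2) = 50%. The exact 95% interval is 6.8% to 93.2%. If true completion were 75%, the chance of 2 or fewer of 4 completing is 0.26. The count is compatible with the planned rate, so the values of p in step 3 are assumptions that span a range, not estimates.

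**5. Precision, under an assumption.** For a paired comparison in completers at two-sided 0.05 and 80% power, the detectable difference is 0.78 SD of the within-participant difference at n = 15 and 1.00 at n = 10. This is an approximation. The Data Analytic Plan specifies a mixed model on repeated ratings, and no SD is given to convert these figures to scale points.

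**The case against.** The best defence is that the conflict is editorial. Two of the three places that size the study say 20, including the approved size. The figure of 15 equals the completer target, so the sentence may have been meant to describe completers. The arithmetic linking 15 and 20 is sound. This has force, and it is why the correction is to the sentence and not to the design. But the sentence does not mention completers, and a maximum is an odd way to express a number that is required. On either reading the wording needs to change.

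Two stronger readings are tempting, and the documents support neither.

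- A reader might infer that the No on deviations is a reporting error. The form asks only about significant deviations. Two losses among four has probability 0.26 at the implied rate, the plan allows five losses in all, and both discontinuations are disclosed with their reason. The answer is a judgement on four people and cannot be shown to be wrong.
- A reader might infer that the trial is heading for about 8 to 12 completers. That treats 2 of 4 as predictive. The low end arises as an expectation only by combining the 15 cap with 50% retention. With 20 enrolled and 75% later completion, 14 are expected, and the chance of finishing with 13 or more is 0.81.

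It is also fair to say that completers need not be the analysed number. The Data Analytic Plan does not restrict the mixed model to completers, so a shortfall does not translate directly into the paired-test figures above.

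**Conclusion.** The concern holds as an internal contradiction with a practical consequence. Under an enrolment cap of 15, the required 15 completers cannot be reached: the ceiling is 13. That result rests only on the reported counts and on reading the sentence as a limit on enrolment; it needs no retention estimate.

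Under 20 enrolled, the target is attainable but, even at the plan's implied 75%, somewhat more likely to be missed than met (0.40). That result assumes independent outcomes with a common completion probability, and that the current participant counts among the 16 still open. The figures at 60% and 50% are conditional scenarios. The loss of precision is indicative only, because it depends on a paired-test approximation and the plan states no precision of its own.

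**What to change.** In the population description, replace the limit of 15 with one statement that matches the other entries: up to 20 enrolled, to obtain 15 completers.

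Beside it, restate the deliverable size as about 10 to 14 expected completers from 20 if later retention is 50% to 75%, and say that this range is conditional on those rates. If a detectable difference is quoted (for example, 0.78 SD of the paired difference at n = 15), label it as an assumption under a paired-test approximation.

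The cost is a wording correction and a less favourable stated size, both of which can go into the current amendment. The approved enrolment of 20, the procedures and the analysis model stay as they are, and the answer on significant deviations can stand.

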protocol with the volunteer and document their consent to the research study. The physician and volunteer will then sign the study consent form.

4) Study procedures will begin after the study physician verifies that the participant meets inclusion/exclusion criteria, understands the medical risks of participation, and is capable of providing informed consent. [name], the senior study physician, will settle any disagreements among the study team as to a volunteer's eligibility, and will make the final decision as to study participation. Behavioral observations and testing will be carried out by one of the study clinicians. In the event of an emergency, one of the study physicians will be available by phone. [name] and other psychologists, nurses, and physicians are around the corner or down a corridor from the outpatient laboratory. We do not test research participants unless we are sure that a physician is available by telephone or by pager in the event of an emergency. A set of emergency procedures, including a list of physicians, telephone and pager numbers is posted in the outpatient laboratory.

Medication: Patients will be administered smoked marijuana at one of the following concentrations: High THC (5-10%)/Low CBD (<1%), Low THC (<1%)/High CBD (>10%), or placebo (0% THC and CBD). The order in which they receive each concentration will be randomized. Participants will complete 1 or 2 sessions per week depending on timing and subject availability. Because of cannabidiol's long terminal half-life (21-33 hours), we are allowing time for drug clearance in between sessions (at least 3 days) to avoid potential carryover effects (Consroe et al., 1991).

General Design: There will be three 4-hour laboratory sessions, which will occur between 0900 and 1300 hr, testing the effect of smoked marijuana on OCD symptoms. Sessions will occur once or twice per week over a period of approximately 3 weeks depending on each participant's availability.

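### The mixed model for this three-session crossover omits session number, and no balancing of condition order is specified, so any session effect can shift the drug-placebo contrasts with little of it reflected in the standard error

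*Combined protocol and SAP*

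**What the plan says.** Study Procedures (General Design) states "There will be three 4-hour laboratory sessions", and there are three conditions, so six orders are possible. Under Medication the whole description of allocation is "The order in which they receive each concentration will be randomized". No block, Latin square, counterbalancing or sequence list appears anywhere. The same paragraph gives a washout: "we are allowing time for drug clearance in between sessions (at least 3 days) to avoid potential carryover effects". That addresses drug left over from the previous session. It does not address differences between a first, second and third visit.

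The Data Analytic Plan (Cannabis Effects) models each outcome "as a function of condition (THC, CBD, placebo), time point, and their interaction", with participant as a random effect and "condition and time as fixed within-subjects factors, the interaction between condition and time, and a random intercept". Time here means the assessment times in Table 1 (-30 to 180 minutes), so it does not stand in for session number. Contrasts will "estimate differences in outcomes between both active cannabis varieties and placebo at different time points". Under Other Effects, age, gender, comorbidity and unspecified other factors are exploratory: "we will nonetheless explore the possibility of such effects by including these factors as covariates in separate analyses". Session and order are not named there. The Data Analysis sentence in Study Procedures, which mentions a repeated-measures ANOVA, names neither.

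**The concern.** Session number is known for every record and is a standard term in a crossover analysis. Ratings could plausibly differ by session. The same scales are completed seven times per session, up to 21 times in all, and session 1 is the first supervised smoking session, for people whose required past use may be as little as one occasion.

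If such an effect exists and the conditions do not fall equally often in each position, part of it appears as a drug effect. The planned model has only a participant intercept. It therefore treats the seven readings in a session as independent given participant, and its standard error is driven by reading-to-reading noise. A shift common to all seven readings is then under-counted. What is at stake is false positives (or a masked effect) in the hypothesised comparisons with placebo.

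**Working it through.** **Plan's own figures.** The plan states 15 completers from 20 enrolled, an implied loss of 1 - 15/20 = 25%. It gives no effect size, SD, power or session effect, so there is no calculation to reproduce. Session effects below are assumptions, in units of the residual SD.

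**Inputs.** 15 completers (Description of Subject Population); 3 sessions and 3 conditions (Study Procedures); 7 assessments per session (Table 1); two-sided alpha of 0.05 (Data Analytic Plan). Simple randomisation is assumed where stated, because no method is given.

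**Step 1: how uneven can position be?** Over the six orders, the session-number difference between two conditions is ±1 in four orders and ±2 in two. Its variance is (4×1 + 2×4)/6 = 2, and the SD of its mean over 15 participants is √(2/15) = 0.365. The exact distribution gives a mean difference of at least 0.5 in about 17% of trials. At least one of the six orders is unused in 36%. The drug-minus-placebo difference in first-session counts has variance 15×2/3 = 10 and SD 3.16. It is 4 or more in 27% of trials.

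**Step 2: the shift against the noise.** The noise SD of a contrast at the average assessment time is √(2/(15×7)) = 0.138. A first-session shift g adds an SD of g×3.16/15. A linear drift of h per session adds h×0.365.

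- g = 0.25: 0.053, total √(0.138² + 0.053²) = 0.148
- g = 0.5: 0.105, total 0.173
- g = 1: 0.211, total 0.252
- h = 0.5: 0.183, total 0.229

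**Step 3: simulation of the planned model.** 15 participants × 3 sessions × 7 times; condition by continuous time; participant fitted as fixed, which is close to equivalent for within-participant contrasts; no true drug effect; no other session-level variation.

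| Assumed session effect | True SD of contrast | Model SE | Type I error, as planned | Type I error, session added |
|---|---|---|---|---|
| none | 0.140 | 0.138 | 0.05 | 0.05-0.06 |
| first session, 0.25 | 0.149 | 0.139 | 0.07 | 0.05 |
| first session, 0.5 | 0.173 | 0.142 | 0.11 | 0.05 |
| first session, 1 | 0.251 | 0.153 | 0.24 | 0.04-0.06 |
| linear, 0.5 per session | 0.227 | 0.150 | about 0.19 | 0.05 |

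The true SDs agree with Step 2. At g = 1 the model SE rises only from 0.138 to 0.153, while the true SD rises to 0.251.

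**Step 4: balance as well.** Blocks of 6 + 6 + 3, with the last three orders forming a Latin square, put each condition in each position five times. With blocks but no session term, type I error is 0.03 to 0.05, conservative when the shift is large. With both, it is 0.046 to 0.051 for first-session shifts of 0 to 1.

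**Step 5: the interaction.** A constant shift within a session does not tilt the slopes over time. The condition-by-time test rejects in about 3% to 5% of simulated trials under these session effects without a session term.

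**Step 6: what remains.** If participants also vary from session to session with an assumed SD of 0.5 residual SD, type I error stays at about 0.20 even with blocks and a session term.

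**The case against.** The strongest reply is that nothing here is shown to go wrong. The documents do not say that order is unbalanced; they say it is randomised and give no method. A reader might infer simple randomisation from that silence, but a balanced list may exist, and with one the excess false positives largely disappear. This stands, so the 17% and the inflated error rates are conditional on simple randomisation.

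Second, a reader might take drift between sessions as expected. No section reports or predicts it. Volunteers come to the laboratory for screening, so session 1 need not be their first contact, and the section on minimising risks says that all currently smoke marijuana. The outcomes are mainly symptom and drug-effect ratings, not performance tests. This also stands: an effect of 0.25 residual SD does little harm, while 0.5 to 1 is material.

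Third, every session has a reading at -30 minutes and the plan tests condition by time. That protects the interaction. It does not protect the time-point contrasts, because the plan does not say they are adjusted for that reading.

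Fourth, a reader might describe the harm as a smaller effective sample size or lost power. That follows for an analysis with one summary per session, where linear drift multiplies the contrast variance by 1 + h², with h in session SDs. The plan specifies a different analysis, in which the main harm is a standard error that is too small.

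**Conclusion.** The point holds as a conditional weakness with a cheap remedy. Session number is absent from a model whose terms are listed, and no balancing of order is specified. If a constant session effect exists and order is simply randomised, the type I error of a drug-placebo contrast at a time point is about 0.07 to 0.24 for first-session shifts of 0.25 to 1 residual SD, and about 0.19 for drift of 0.5 per session. These figures assume 15 completers and no participant-by-session variation.

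Two stronger readings are not supported. The contrasts are not biased over repeated trials, because randomisation of order prevents that; the shift is a chance imbalance in the one trial that is run. Nor is the whole analysis undermined, since the condition-by-time test is largely unaffected. The omission is certain from the text; the size of its effect is not.

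**What to change.** Add session number (1, 2, 3) as a categorical fixed effect to the mixed model under Cannabis Effects, for all outcomes. State the randomisation method. If order is not already balanced, allocate remaining participants in blocks over the six orders.

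Enrolment was ongoing with 5 of 20 enrolled at this continuing review, so most orders could still be blocked, and the model term also covers participants already tested. Keep the term even with blocks: 2 of the 5 have discontinued, and such losses disturb any balance.

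The cost is 2 degrees of freedom and a new allocation list. With no session effect, the contrast SE rises from about 0.139 to 0.144 residual SD under simple randomisation (some 3% to 4%), and hardly at all with blocks. A participant-by-session random effect should be considered separately, since the session term does not supply it.

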- 6. Patient has not smoked marijuana more than once per day over the preceding 8 weeks.
Clinical Interview and urine toxicology
- 8. Each patient must have a level of understanding sufficient to provide written informed consent to all required study tests and procedures.
Clinical interview
- 9. Women who are practicing an effective form of birth control (e.g. hormonal contraception or barrier methods).
Clinical interview

Create or insert table to describe the exclusion criteria and methods to ascertain them

- 1. First degree relative with schizophrenia
Psychiatric evaluation
- 2. Presence of psychotic symptoms or lifetime history of schizophrenia, bipolar disorder, substance-induced psychotic disorder, or psychosis due to a general medical condition.
Psychiatric evaluation/SCID
- 3. Current, eating disorder
Psychiatric

| | |
|---|--|
| | evaluation |
| 4. Major Depressive Disorder or other current psychopathology requiring medical intervention | Psychiatric evaluation |
| 5. Severely depressed patients with HDRS (Hamilton Depression Rating Scale) score greater than 25 or judged clinically to be at risk of suicide | Psychiatric evaluation/SCID and HDRS |
| 6. Female patients who are either pregnant or nursing | Clinical interview, medical examination, and blood pregnancy test |
| 7. Patients planning to commence cognitive-behavioral therapy during the period of the study or those who have begun cognitive-behavioral therapy within 8 weeks prior to enrollment | Clinical interview |
| 8. Patients receiving psychotropic medication other than clomipramine or selective SRIs. Patients taking clomipramine or a selective SRI must be on a stable dose for 6 weeks prior to study entry and must not plan to alter their regimen during the period of the study. | Clinical interview |
| 9. Patients who report using any illicit substances other than marijuana within 3 months prior to study entry or who have a urine toxicology screen positive for any substance other than marijuana. | Clinical interview |
| 10. Presence of significant medical illness (e.g. diabetes, cardiovascular disease, hypertension, clinically significant laboratory abnormalities, LFTs>1.5x upper limit of normal), resting blood pressure >140/90 | Medical history, physical examination, laboratory tests, 12-lead ECG, Mantoux test |
| 11. History of heart disease | Clinical interview, abnormal ECG |
| 12. Current parole or probation | Self-report during interview |

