Laboratory Sessions: Participants will be instructed that they should not smoke either marijuana or cigarettes on the morning of a session (beginning at midnight). We will do a carbon monoxide (CO) test upon their arrival in the laboratory to verify nothing was recently smoked. Participants will also be given a breathalyzer test to ensure that they did not drink alcohol prior to arrival. At each visit, urine samples will be tested for drug use, and, for women of child-bearing age, for pregnancy. Subjects who are found to be pregnant will be discontinued from the study, but will receive payment for those procedures that they have already completed. Participants with high COs or those testing positive for drugs other than marijuana will be re-scheduled and possibly excluded from further participation. Patients will then receive either high THC (5-10%)/low CBD (<1%) marijuana, low THC (<1%)/high CBD (>10%) marijuana, or placebo (0% THC and CBD). The marijuana used in the study will be provided by the NIDA. We will guide participants through smoking individual puffs of marijuana using cue-dosing procedures until 50% of the cigarette has been smoked. Specifically, for each puff, participants will be instructed to inhale for 5 seconds and hold each puff in the lungs for 10 seconds. There will be approximately a 40-second interval between each puff. For the first hour after marijuana administration, clinical ratings, scales, and BP/HR will be obtained every 20 minutes. During the second hour, these measures will be repeated once every half-hour, and then again at the conclusion of the third hour (see Table 1). The session will end after the third hour. Participants will be allowed to leave the facility when they pass the field sobriety test, and will be instructed not to drive a car or use other drugs or alcohol for at least 8 hours after marijuana administration.

Table 1. Session Schedule

| TIME (min) | EVENT |
|------------|--|
| -50 | CO, collect urine, breathalyzer, start breakfast |
| -30 | Finish breakfast (set timer for 30 min), balance, TLFB, BP/HR, VAS, YBOCCS, STAI |
| 0 | Marijuana administration |
| 20 | BP/HR, VAS, YBOCCS, MRF, STAI |
| 40 | BP/HR, VAS, YBOCCS, MRF, STAI |
| 60 | BP/HR, VAS, YBOCCS, MRF, STAI |
| 90 | BP/HR, VAS, YBOCCS, MRF, STAI |
| 120 | BP/HR, VAS, YBOCCS, MRF, STAI |
| 180 | BP/HR, VAS, YBOCCS, MRF, STAI, Field Sobriety Test, participant discharge |

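### Pre-session abstinence and the entry limit name smoked marijuana only, and no stated action follows evidence of same-morning cannabinoid use by another route

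*Combined protocol and SAP*

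**What the plan says.** All references are to the combined protocol and SAP.

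- **Abstinence instruction** (Study Procedures, Laboratory Sessions): "Participants will be instructed that they should not smoke either marijuana or cigarettes on the morning of a session (beginning at midnight"). No other route is named.
- **Entry limit** (inclusion criterion 6): "Patient has not smoked marijuana more than once per day over the preceding 8 weeks".
- **CO test** (Laboratory Sessions): "We will do a carbon monoxide (CO) test upon their arrival in the laboratory to verify nothing was recently smoked".
- **Urine test** (Laboratory Sessions): "At each visit, urine samples will be tested for drug use". The panel is not given, and Assessment Instruments lists the urinalysis as qualitative. At entry, exclusion 9 applies only to a "urine toxicology screen positive for any substance other than marijuana".
- **Action on these checks** (Laboratory Sessions): "Participants with high COs or those testing positive for drugs other than marijuana will be re-scheduled and possibly excluded from further participation".
- **Pre-dose assessments** (Table 1, -30 min): "balance, TLFB, BP/HR, VAS, YBOCCS, STAI". No rule is given for acting on what the TLFB shows.
- **Medication** (exclusion 8): psychotropic drugs are barred apart from clomipramine and selective SRIs. Cannabinoid and CBD products are not named.

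**The concern.** The hypothesis sets THC-rich and CBD-rich marijuana against a placebo with no THC or CBD. A participant's own THC or CBD is the same kind of exposure as the treatment, so its absence on arrival matters more here than in most trials. The protocol evidently intends drug-free arrival: it breathalyses for alcohol and separates sessions by at least 3 days because of CBD's half-life. Its instruction for after the session is also broader, covering other drugs and alcohol without reference to route. The pre-session rule covers only one route.

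Own use could lower the -30 min symptom scores, make sessions differ for reasons unrelated to condition and, if effects saturate, reduce the room for the study drug to act. The Data Analytic Plan models condition, time and their interaction and has no term for own use. With 15 planned completers, extra session-to-session variation is costly, and own use that was never asked about cannot be adjusted for afterwards.

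**Working it through.** The plan gives no power, effect size or SD, and no rate of non-smoked use, so there is no stated figure to reproduce.

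**1. Follow one case through the rules.** A participant takes an edible or CBD oil at 08:00 and arrives at 09:00.
- Abstinence instruction: nothing was smoked, so it is not breached as worded.
- CO: by its stated purpose it checks for smoking, so it does not address this use.
- Urine: it may read marijuana by any route, and whether it reads CBD is not stated. A marijuana-positive result has no stated consequence. A qualitative result also cannot separate that morning's use from earlier use or from the previous study dose.
- TLFB at -30 min: it may record marijuana use by self-report, but no action follows. CBD products are not mentioned.

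The session goes ahead under the text as written.

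**2. Illustrative size.** Assumptions: own use affects each session independently with probability p, with the same effect E as the study drug. Since no rate is given, p runs from 1% to 20%.

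*Additive effects.* The active-placebo difference gains noise with SD = sqrt(2p(1-p)) x E.

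| p | SD of added noise | Mean difference under full saturation |
|---|---|---|
| 0.01 | sqrt(0.0198) E = 0.14E | 0.99E |
| 0.02 | sqrt(0.0392) E = 0.20E | 0.98E |
| 0.10 | sqrt(0.18) E = 0.42E | 0.90E |
| 0.20 | sqrt(0.32) E = 0.57E | 0.80E |

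The noise column is an upper case. The Data Analytic Plan evaluates changes in each outcome, and an effect already present and constant from -30 min onward largely cancels in change from baseline. Only an effect still rising or wearing off during the session remains.

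*Full saturation.* The mean difference is (1-p)E on either scale. On raw scores, active sessions reach E and placebo sessions average pE. On change from baseline, placebo sessions show 0 and active sessions average (1-p)E, because an affected active session has no further room to change. Dilution therefore does not cancel.

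**3. What a midnight cut-off can achieve.** Use the protocol's CBD half-life of 21-33 h and terminal-phase decay only: fraction remaining = 0.5^(t/half-life).
- Midnight to dosing, taking arrival at 09:00 and dosing 50 minutes later (t = 9.83 h): 0.72 to 0.81.
- Minimum gap between sessions (t = 72 h): 0.09 to 0.22.

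An any-route midnight rule closes the same-morning gap but does not make the placebo session free of CBD.

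**The case against.** Several stronger readings are tempting, and the documents do not support them.

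- **That neither arrival check can detect non-smoked use.** The urine panel is unstated, and the reference to drugs other than marijuana implies that marijuana can be read, with no limit by route. What is missing is a consequence and a way to date the use. Non-detection of CBD would be an assumption.
- **That same-morning use is permitted and goes unrecorded.** The TLFB, balance test, vital signs and VAS all precede dosing and are partial checks. The TLFB has no stated route restriction. Exclusion 8 may reach some CBD products, which the risk section itself calls a medication, and non-compliance is a ground for discontinuation. The consent pages and the separate screening protocol are not available here and may say more. The supportable statement is that such use is not clearly prohibited.
- **That the contrast is biased in one direction.** Order is randomised within participant and own use precedes dosing, so it should fall on all three conditions alike on average. Chance imbalance is possible with 15 completers.
- **That 10-20% of sessions would be affected.** Nothing supports any particular rate. Among occasional smokers told not to smoke that morning, it may be 1-2% or less.

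It is also fair to object that the fix keeps the midnight cut-off and relies on self-report, so it cannot secure a cannabinoid-free placebo session. That limits what the change achieves. It does not remove the gap: a rule meant to ensure drug-free arrival names one route, and the checks that might reveal other use lead nowhere.

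**Conclusion.** The point holds in a limited form. The instruction and inclusion 6 cover smoked marijuana only, CO addresses smoking only, and neither a marijuana-positive urine nor a TLFB report of same-morning use has a stated consequence. The probable cost is noise and some dilution of the active-placebo contrast. The figures (shrinkage of 1-20% under full saturation; additive noise of at most 0.14E-0.57E) rest on an assumed rate of 1-20%, independence between sessions, and own use being as strong as the study drug. They show scale and are not estimates. This is a modest weakness and does not by itself invalidate the comparison, but it should be corrected because the change is nearly free and lost information on own use cannot be recovered.

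**What to change.** 1. Extend the midnight instruction to cannabis, THC and CBD products by any route, keeping cigarettes.
2. Count use by any route in inclusion criterion 6 for participants not yet enrolled. At the continuation report 5 of the approved 20 had enrolled, leaving up to 15.
3. At the -30 min TLFB already in Table 1, ask about non-smoked cannabis and CBD products since the last visit, including that morning, and record the answer.
4. Handle reported same-morning use as a high CO is handled now, by re-scheduling the session.

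The cost is rewording one instruction and one criterion, a question or two in an interview listed at 3 minutes, and an occasional re-scheduled session. The change relies on self-report and does not address use before midnight, which is a separate matter to reconcile with the protocol's own reasoning for the 3-day gap between sessions.
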